12. AMENDMENTS

Protocol modifications, except those intended to reduce immediate risk to study subjects, may be made only by Pfizer (or specified designee). A protocol change intended to eliminate an apparent immediate hazard to subjects may be implemented immediately.

Any permanent change to the protocol must be handled as a protocol amendment. The written amendment must be submitted to the IRB/IEC and the Investigator must await approval before implementing the changes. Pfizer or specified designee will submit protocol amendments to the appropriate regulatory authorities for approval.

If in the judgment of the IRB/IEC, the Investigator, and/or Pfizer, the amendment to the protocol substantially changes the study design and/or increases the potential risk to the subject and/or has an impact on the subject's involvement as a study subject, the currently approved written informed consent form will require similar modification. In such cases, informed consent will be renewed for subjects enrolled in the study before continued participation.

13. STUDY REPORT AND PUBLICATIONS

Pfizer (or specified designee) is responsible for preparing and providing the appropriate regulatory authorities with clinical study reports according to the applicable regulatory requirements.

The publication policy is discussed in the investigator's Clinical Research Agreement.

14. STUDY DISCONTINUATION

Both Pfizer and the Principal Investigator reserve the right to terminate the study at the Investigator's site at any time. Should this be necessary, Pfizer or a specified designee will inform the appropriate regulatory authorities of the termination of the study and the reasons for its termination, and the Principal Investigator will inform the IRB/IEC of the same. In terminating the study, Pfizer and the Principal Investigator will assure that adequate consideration is given to the protection of the subjects' interests.

15. DATA PROTECTION

All parties will comply with all applicable laws, including laws regarding the implementation of organizational and technical measures to ensure protection of participant data.

Subjects' personal data will be stored at the study site in encrypted electronic and/or paper form and will be password protected or secured in a locked room to ensure that only authorized study staff have access. The study site will implement appropriate technical and organizational measures to ensure that the personal data can be recovered in the event of disaster. In the event of a potential personal data breach, the study site will be responsible for determining whether a personal data breach has in fact occurred and, if so, providing breach notifications as required by law.

To protect the rights and freedoms of subjects with regard to the processing of personal data, participants will be assigned a single, participant specific numerical code. Any subject records or data sets that are transferred to the sponsor will contain the numerical code; subject names will not be transferred. All other identifiable data transferred to the sponsor will be identified by this single, subject specific code. The study site will maintain a confidential list of subjects who participated in the study, linking each subject's numerical

code to their actual identity and medical record ID. In case of data transfer, the sponsor will protect the confidentiality of subjects' personal data consistent with the clinical study agreement and applicable privacy laws.

Information technology systems used to collect, process, and store study-related data are secured by technical and organizational security measures designed to protect such data against accidental or unlawful loss, alteration, or unauthorized disclosure or access.

The sponsor maintains SOPs on how to respond in the event of unauthorized access, use, or disclosure of sponsor information or systems.

When subject data are to be deleted, the investigator will ensure that all copies of such data are promptly and irrevocably deleted from all systems.

16. APPENDICES

16.1. Appendix 1 – Definition of Migraine and Headache Days

A **Migraine Day** is defined as any calendar day which the subject experiences a qualified migraine headache (onset, continuation or recurrence of the migraine headache). A qualified migraine headache is defined as a migraine with or without aura, lasting for ≥ 30 minutes, and meeting either Criteria A or B:

A. ≥ 2 of the following pain features:

- Unilateral location,
- Pulsating quality (throbbing),
- Moderate or Severe headache pain intensity,
- Aggravated by or causing avoidance of routine physical activity (e.g., walking or climbing stairs)

\geq of the following associated symptoms:

- Nausea and/or Vomiting,
- Photophobia and phonophobia

During the Observational Phase, DBT Phase, and OLE Phase, if the subject takes an acute migraine-specific medication (i.e., triptan, ergotamine, lasmiditan, or ubrogepant) to treat a headache (or aura) on any calendar day, then it will be counted as a migraine day regardless of the duration and pain features/associated symptoms.

Of note, the use of ergotamine is prohibited throughout the entire duration of the study. However, all dosing of acute migraine-specific medication (i.e., triptan, ergotamine, lasmiditan, and ubrogepant) must be reported within the eDiary(DBT) and the Concomitant Medication paper diary, to accurately inform the occurrence of a “migraine day”.

A moderate or severe migraine day is a migraine day with a migraine reported with moderate or severe headache pain intensity.

Migraine Attack: An episode of any qualified migraine headache. The following rules will be used to distinguish an attack of long duration from two attacks, or to distinguish between attacks and relapses:

- a) A migraine attack that is interrupted by sleep, or temporarily remits, and then recurs within 48 hours (i.e., ≤ 48 hours between the start of the migraine attack to the time of the recurrence) will be considered as one attack and not two.

- b) An attack treated successfully with medication but with relapse within 48 hours (i.e., ≤ 48 hours between the start of the migraine attack to the time of the recurrence) will be considered as one attack.

Definition of Headache Days

A Headache Day is any calendar day in which the subject experiences a qualified headache (initial onset, continuation, or recurrence of the headache). A qualified headache is defined as:

- A qualified migraine headache (including an aura-only event that is treated with acute migraine-specific medication (i.e., triptan, ergotamine, lasmiditan, or ubrogepant), or
- A qualified non-migraine headache, which is a headache that lasts ≥ 30 minutes and is not a qualified migraine headache, or
- A headache of any duration for which acute headache treatment is administered.

16.2. Appendix 2 – Recognized, Orally-Administered Migraine-Preventive Medications

Eligible subjects must have experienced, within 10 years of the Screening Visit, inadequate response (due to lack of efficacy or prior intolerance) to specified agents across 2-4 of the following categories of recognized, orally-administered migraine-preventive medications where at least one example of prior inadequate response is due to lack of efficacy or prior intolerance (not contraindication). Within Categories 1-7 this list of medications is specific and exclusive of other medications. Individuals with a history of inadequate response (due to a lack of efficacy, prior intolerance or contraindication) to agents across >4 of the following categories are to be excluded from this study.

- Category 1 Valproic acid: **specifically, divalproex sodium, sodium valproate**
- Category 2 Other anticonvulsant: **specifically, gabapentin, topiramate**
- Category 3 Beta blocker: **specifically, atenolol, bisoprolol, metoprolol, nadolol, propranolol, timolol**
- Category 4 Tricyclic antidepressant: **specifically, amitriptyline**
- Category 5 Serotonin-norepinephrine reuptake inhibitor (SNRI): **specifically, desvenlafaxine, venlafaxine**
- Category 6 Calcium-channel blocker: **specifically, flunarizine, verapamil**
- Category 7 Angiotensin blocker (angiotensin-converting enzyme [ACE] inhibitor, angiotensin II receptor blocker [ARB]): **specifically, candesartan, lisinopril**
- Category 8 Other: **locally-approved, or otherwise recognized standard of care, oral medications for the preventive treatment of migraine (e.g., methysergide, oxetrone, pizotifen).** If the subject has experienced inadequate response to a medication under this category, supporting documentation is required from the site noting the national or regional published guidelines as to why this medication had been included.

Inadequate Response is defined as meeting any of the following criteria:

- Lack of Efficacy:
 - When previous treatment with a recognized, orally-administered, migraine-preventive medication has yielded no meaningful reduction in headache frequency (e.g., <50% reduction in frequency and/or severity of monthly migraine days) after administration of the respective medication for an adequate period of time (at least 2 - 3 months) at generally accepted therapeutic dose(s) based on the investigator's assessment and documented within the medical/pharmacy record. If the Principal Investigator is not the treating physician and the medical record is not available for documentation purposes, the Principal Investigator can interview the treating physician to confirm the above information and document the interview with date and his/her signature.

When the medical/pharmacy records are available indicating the subject use of previous treatment with a recognized, orally-administered, migraine-preventive medication but there is no documentation on the lack of efficacy, an interview with the subject and documentation with date and time will suffice. This interview must probe on the same indicators of efficacy (e.g., reduction in migraine headache day frequency and severity) described above and such evidence of unsatisfactory efficacy based on interview responses must be documented in sufficient detail to support the conclusion of lack of efficacy.

- Prior Intolerance:
 - When prior treatment with a recognized, orally-administered, migraine-preventive medication has been previously interrupted because of an adverse event(s) that made continuation of the drug unacceptable, as determined by the Principal Investigator and documented within the medical/pharmacy record. If the Principal Investigator is not the treating physician and the medical/pharmacy record is not available for documentation purposes, the Principal Investigator can interview the treating physician to confirm the above information and document the interview with date and his/her signature. When the medical/pharmacy records are available indicating the subject's use of previous treatment with a recognized, orally-administered, migraine-preventive medication but there is no documentation on the lack of prior intolerance, an interview with the subject and documentation with date and time will suffice. This interview must capture a detailed description of the adverse effects from the prior prophylaxis treatment and the reasons the participant found it to be intolerable (e.g., severity, duration, impact on function, etc). Such evidence based on interview responses must be documented in sufficient detail to support the conclusion of intolerance to previous treatment.
- Contraindication:
 - When a recognized, orally-administered, migraine-preventive medication is contraindicated or otherwise considered inadvisable in accordance with locally recognized labelling, practice guidelines, and/or the current standard of care, as determined by the Principal Investigator with rationale documented within the medical record. If the Principal Investigator is not the treating physician and the medical record is not available for documentation purposes, the Principal Investigator can interview the treating physician to confirm the above information and document the interview with date and his/her signature. When the medical records or other objective evidence on screening are available indicating the subject's use of previous treatment with a recognized, orally-administered, migraine-preventive medication but there is insufficient documentation on the contraindication, a supplemental interview with the subject and documentation with date and time will suffice.

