1.1.2. Product Development Background

Details of the clinical and preclinical studies are provided in the most current Investigator Brochure.⁴ A summary of the relevant data to the study are presented below.

Rimegepant is approved for the acute treatment and prevention of episodic migraine in the United States (US), United Kingdom (UK), and European Union (EU) and is well tolerated in humans when given as a single oral dose of 75 mg for the acute treatment of migraine and at a dose of 75 mg every other day (EOD) for the prevention of episodic migraine. The efficacy, safety, and tolerability of rimegepant for the acute and preventive treatment of migraine in the pediatric population is currently being evaluated.

As of 26 February 2024, it is estimated that 12,135 participants have been involved in Rimegepant clinical development studies and approximately 6630 participants have received Rimegepant at any dose. Collectively, the current data demonstrates a favorable benefit-risk profile for rimegepant in the acute and preventive treatment of migraine.

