1.3.1. Study Design Rationale

This is a multicenter, randomized, double-blind, placebo-controlled evaluation of the safety and efficacy of rimegepant (75 mg ODT taken every other day) for prophylaxis in adults with a history of inadequate response to a variety of available oral migraine-preventive medications from different mechanistic classes. The double-blind, placebo-controlled, parallel group design to assess the efficacy, safety and tolerability of rimegepant as preventative treatment is in accordance with international guidelines.¹¹ Up to approximately

600 eligible subjects will be randomized in a 1:1 ratio to blinded rimegepant (75 mg) or matching placebo and stratified by: 1) the number of migraine days reported to have occurred during the 28-day Observation Phase (4-7 or 8-14); and 2) the number of recognized, orally-administered, preventive medication categories with previous inadequate response within 10 years of the Screening Visit (due to lack of efficacy, prior intolerance, or contraindication) (2 vs. 3-4 categories).

During the 12-week DBT Phase, subjects will be instructed that they must take one tablet of blinded study drug every other calendar day (EOD). If subjects have a migraine during the DBT Phase, permitted acute migraine medication (see Section 16.4, Appendix 4) may be used, as needed, and in accordance with the standard of care, to manage acute attacks regardless if the migraine occurs on a study drug dosing day or non-dosing day. **Blinded study drug is NOT to be used for the treatment of acute migraine attacks during the DBT Phase.**

Upon successful completion of the DBT Phase, eligible subjects will be given the opportunity to enroll into a 12-week OLE Phase. It is estimated that approximately 480 subjects will enter the OLE Phase of the study.

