 - i. Biologic migraine medication (such as CGRP antagonist monoclonal antibodies) taken within 6 months (24 weeks) prior to the Screening Visit
 - ii. Botulinum toxin injections (e.g., Botox®) used for the prevention of migraine taken within 3 months (12 weeks) prior to the Screening Visit
- b) Non-Narcotic Analgesics (e.g., nonsteroidal anti-inflammatory drugs [NSAIDs] or paracetamol [acetaminophen] taken ≥ 15 days per month during the 3 months (12 weeks) prior to the Screening Visit
- c) Cefaly™ or any other device for migraine prevention or treatment within 3 months (12 weeks) prior to the Screening Visit
- d) Ergotamine taken ≥ 10 days per month on a regular basis for ≥ 3 months (≥ 12 weeks) in the year prior to the Screening Visit
- e) Narcotic, such as opioid (e.g., morphine, codeine, oxycodone, hydrocodone) or barbiturate (e.g., butalbital), taken for ≥ 4 days per month during the 3 months (12 weeks) prior to the Screening Visit

- f) Permitted acute migraine medication taken ≥ 15 days per month for a non-headache indication during the 3 months (12 weeks) prior to the Screening Visit (see Section 5.5)
 - i. Low dose aspirin (e.g., up to 100 mg daily) for documented cardiovascular prophylaxis is allowed.

Note: See Section 5.7 and Section 16.3 Appendix 3 for further details related to prohibited medications and devices

7. Other Exclusion Criteria

- a) Non-compliance with or inability to complete eDiary during Observation Phase. Subjects with less than 24 completed eDiary reports during the first 28 days in the Observation Phase will not be considered for participation due to non-compliance with the eDiary.
- b) Exposure to non-biological investigational agents within 30 days prior to the Screening Visit
- c) Exposure to biological investigational agents (including monoclonal antibodies) within 6 months (24 weeks) prior to the Screening Visit
- d) Previous enrollment in any multiple dose BHV3000 (rimegepant) study, such as BHV3000-201, BHV3000-305, BHV3000-405, or BHV3000-406, regardless of the number of doses taken. Subjects may be considered for BHV3000-407 if the subject participated in any of the following single dose studies: BHV3000-301, BHV3000-302, BHV3000-303, but did not participate in any multiple dose rimegepant study. Note that subjects who were considered screen failures in a past BHV3000 study may be considered after discussion with the Sponsor and written approval is received.

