16.3. Appendix 3 – Prohibited and Restricted Concomitant Medications and Devices

Use of the following medications and devices is prohibited or restricted during the study (i.e., starting from the Screening Visit and through the Follow-up Week 2 Visit), unless otherwise specified.

- Use of the following recognized migraine-preventive medications within 30 days prior to the Screening Visit and throughout the study, unless otherwise specified:
 - All prophylactic treatments targeting the CGRP pathway
 - Oral small molecules (e.g., atogepant, non-study rimegepant, etc.)
 - Injectable monoclonal antibodies (e.g., eptinezumab, erenumab, fremanezumab, galcanezumab, etc.)- these particular medications must be discontinued at least **6 months** (24 weeks) prior to the Screening Visit and throughout the study
 - ACE inhibitors / Angiotensin receptor blockers: candesartan, lisinopril
 - Alpha-adrenergic agonists: clonidine, guanfacine
 - Antidepressants: amitriptyline, desvenlafaxine, duloxetine, milnacipran, nortriptyline, protriptyline, venlafaxine
 - Antiepileptics: gabapentin, topiramate, valproic acid (sodium valproate, divalproex sodium)
 - Beta-blockers: atenolol, bisoprolol, metoprolol, nadolol, nebivolol, pindolol, propranolol, timolol
 - Calcium channel blockers: flunarizine, lomerizine, nifedipine, nimodipine, verapamil
 - Onabotulinumtoxin A (Botox[®]) taken within **3 months** (12 weeks) prior to the Screening Visit and throughout the study
 - Serotonin antagonists: methysergide, oxetrone, pizotifen
 - Vitamins / Supplements: butterbur, feverfew, magnesium citrate (≥ 600 mg/day), riboflavin (Vitamin B2; ≥ 100 mg/day)
 - Other locally-approved, or otherwise recognized standard of care, medications used for the preventive treatment of migraine, unless otherwise specified
- Note: Stable use (consistent dosing frequency and strength at least 3 months [12 weeks] prior to the Screening Visit and afterward) of the above migraine preventive medications for non-headache indication is allowed, unless otherwise specified. The above medications are NOT permitted to be newly initiated at any time during the course of the study (e.g., Screening, DBT, or OLE Phases)

- All devices and/or invasive interventions used for the preventive treatment of migraine (e.g., nerve blocks, occipital nerve stimulators, transcranial magnetic stimulation, etc.) administered within 3-months(12 weeks) of the Screening Visit and throughout the study

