#### **9.4.2 Number of ROM Medication Categories With Previous Inadequate Response**

The number of ROM medication categories with previous inadequate response is calculated as the sum across categories in which there is  $\geq 1$  medication with previous inadequate response due to (1) lack of efficacy within 10 years of the Screening Visit, (2) prior intolerance within 10 years of the Screening Visit, or (3) contraindication.

Analyses are based on medications in the migraine-preventive medication category of “recognized orally-administered migraine-preventive medication” from the Previous Experience With or Documented Contraindication to Prophylactic Migraine Medications CRF (see Section 9.4.1).

Medications with previous inadequate response due to lack of efficacy within 10 years of the Screening Visit are those that meet both of the following criteria:

- Inadequate response reason of “lack of efficacy”
- Screening visit date – 3651 days  $\leq$  nonstudy medication imputed start date or imputed end date  $\leq$  screening visit date – 1 day (see Section 7.1).

Medications with previous inadequate response due to prior intolerance within 10 years of the Screening Visit are those that meet both of the following criteria:

- Inadequate response reason of “prior intolerance”
- Screening visit date – 3651 days  $\leq$  nonstudy medication imputed start date or imputed end date  $\leq$  screening visit date – 1 day (see Section 7.1).

Medications with previous inadequate response due to contraindication are those with either (1) inadequate response reason of “contraindication” or (2) nonmissing contraindication reason.

- Medications with previous inadequate response due to contraindication due to hypersensitivity are those with contraindication reason of “hypersensitivity”.
- Medications with previous inadequate response due to contraindication due to other reason are those with contraindication reason of “other”.

- Medications with previous inadequate response due to contraindication reason not reported are those with both (1) inadequate response reason of “contraindication” and (2) missing contraindication reason.

If the number of ROM medication categories with previous inadequate response is NOT  $\geq 1$ , then the following apply:

- The number is set to 0 if either of the following criteria is met:

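### Failure of prescribed rimegepant can count towards eligibility through Category 8, while exclusion 7d bars only earlier multiple-dose trial enrolment

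*Protocol*

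**What the plan says.** Protocol 5.2 (criterion 1g) requires prior inadequate response within ten years of screening across two to four categories of oral preventive. At least one response must be lack of efficacy or intolerance rather than contraindication. Appendix 2 (16.2) defines eight categories. Categories 1 to 7 are closed drug lists. Category 8 is not: "locally-approved, or otherwise recognized standard of care, oral medications for the preventive treatment of migraine (e.g., methysergide, oxetrone, pizotifen" are examples only. Its one added condition is that "supporting documentation is required from the site noting the national or regional published guidelines as to why this medication had been included".

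Three other places bear on rimegepant:

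- Protocol 1.1.2: "Rimegepant is approved for the acute treatment and prevention of episodic migraine in the United States (US), United Kingdom (UK), and European Union (EU").
- Appendix 3 (16.3), among recognized preventives not allowed from 30 days before screening onwards: "Oral small molecules (e.g., atogepant, non-study rimegepant, etc".)
- Exclusion 7d (Protocol 5.3): "Previous enrollment in any multiple dose BHV3000 (rimegepant) study, such as BHV3000-201, BHV3000-305, BHV3000-405, or BHV3000-406, regardless of the number of doses taken". The same item allows entry after three named single-dose studies.

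SAP 9.4.2 uses the same scheme: "The number of ROM medication categories with previous inadequate response is calculated as the sum across categories in which there is" at least one drug with such a response. Category 8 is one of the eight categories listed in SAP 9.4.1.

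**The concern.** The trial asks whether rimegepant helps people poorly served by existing oral preventives. On the text as written, one of the failures that brings a subject in can be a failure of rimegepant itself. Intolerance counts as well, so a subject who stopped prescribed rimegepant because of adverse events gains a category in a trial that also studies its tolerability.

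The handling of rimegepant history is also uneven. A single dose in an earlier multiple-dose study excludes a subject. A full failed course on prescription does not exclude, and it counts in the subject's favour. If such subjects benefit less than others, the average treatment difference shrinks and the enrolled population is harder to describe.

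**Working it through.** **The plan's own figure.** Protocol 9.1 and SAP 5 give a difference of 1.0 day, SD 3.6, 280 per group and two-sided alpha 0.05.

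- SE = 3.6 × √(2/280) = 0.304.
- Power = Φ(1.0/0.304 − 1.96) = 90.8%, against the stated value of roughly 90%. The figure reproduces.

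**Does rimegepant meet the Category 8 wording?** It is oral, and Protocol 1.1.2 calls it approved for prevention in the US, UK and EU. It is on none of the closed lists in Categories 1 to 7. Appendix 3 treats it as a recognized preventive. Nothing in Category 8 excludes it.

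**What could stop such a subject?**

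- The washout (exclusion 6a and Appendix 3) covers only 30 days before screening, so an earlier failed course passes.
- Exclusion 7d covers study enrolment, not prescription.
- The guideline documentation tests whether a drug is recognized, not whether it is the study drug.
- Exclusions 3a (allergy) and 7h (investigator's opinion) could be used but do not require it.
- The relevant deviations in SAP 9.1 look for treatment in an earlier multiple-dose rimegepant study. They do not look for prescribed use.

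**Applying the counting rule.** Each listed drug goes to its own category, rimegepant goes to Category 8, and distinct categories are counted.

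| Documented inadequate response | Categories | Within 2 to 4? |
|---|---|---|
| Rimegepant only | 1 | No |
| Rimegepant and atogepant | 1 (both Category 8) | No |
| Rimegepant and propranolol | 2 | Yes |
| Rimegepant, propranolol and topiramate | 3 | Yes |

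In the third row rimegepant decides eligibility, because propranolol alone counts as one. The propranolol entry may even be a contraindication, since 1g asks for only one response due to lack of efficacy or intolerance. Rimegepant could then be the only preventive the subject had actually taken and failed.

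**Effect on the primary contrast.** If a share f of subjects are prior rimegepant failures with mean benefit d, and the rest have the planned 1.0 day, the average difference is (1 − f) × 1.0 + f × d. Neither f nor d is in the documents, so no loss can be calculated. Protocol 9.1 does not mention such subjects.

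**The case against.** The best defence is that several steps stand between a rimegepant failure and randomisation: a second category, documented guideline support, documentation of the failure under Appendix 2, and the investigator's judgement under 7h. This stands as a limit on how often it happens, but none of these steps rules it out. The purpose of 7d is not stated, and the protocol does not bar prior rimegepant exposure as such. The gap is therefore an omission, not a breach of a stated rule.

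A reader might infer more than the text supports:

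- **Any approved oral preventive qualifies a subject.** It does not. Drugs named in Categories 1 to 7 stay in their own category, and Category 8 adds at most one.
- **One drug class is counted twice.** Appendix 3 names drugs missing from the closed lists, for example in "Antidepressants: amitriptyline, desvenlafaxine, duloxetine, milnacipran, nortriptyline, protriptyline, venlafaxine", so amitriptyline and nortriptyline might seem to make two categories. Whether nortriptyline counts under Category 8 is open, because all three Category 8 examples come from a class absent from Categories 1 to 7. Protocol 1.3.1 does speak of "a variety of available oral migraine-preventive medications from different mechanistic classes", but that is description, not a criterion. The categories are not mechanistic classes in any case: valproate is separate from other anticonvulsants, while ACE inhibitors and ARBs are pooled. This needs a clarification of wording only.
- **Some subjects are in the wrong stratum.** Stratum 2 is defined by the category count, and the SAP derives it by the same rule. A subject counted through Category 8 is in the stratum as defined.
- **Power is materially reduced.** That needs a value for the share and an assumption of no benefit. Appendix 2 gives less than 50% reduction as its example of lack of efficacy, so a subject below that mark could still gain a day. Intolerance says nothing about efficacy.

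Part of the remedy also exists. SAP 6.2.5.4 already tabulates failed oral preventives by reason and preferred name, so rimegepant recorded there would be visible.

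**Conclusion.** The point holds in a limited form. Documented lack of efficacy of, or intolerance to, prescribed rimegepant can supply one of the two to four qualifying categories, and exclusion 7d does not prevent this. The conclusion rests on reading Category 8 as worded and on a site being able to cite a guideline that supports rimegepant for prevention, which cannot be checked from the documents.

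The number of subjects affected and the loss of effect are unknown. The stated power is not shown to be wrong. Allocation is randomised and blinded, so these subjects do not bias the comparison between arms. What is affected is who the population represents and, possibly, the size of the effect seen.

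**What to change.** 1. In Category 8 of Appendix 2, state that rimegepant does not count as a qualifying medication.
2. Reconcile exclusion 7d with this, so that documented prior inadequate response to non-study rimegepant is treated consistently with earlier multiple-dose study enrolment.
3. In the same edit, say whether unlisted drugs of a class in Categories 1 to 7 count under Category 8.
4. For subjects already randomised, identify before unblinding those with rimegepant recorded as lack of efficacy or prior intolerance on the Previous Experience CRF. Search both branches of that form (recognized oral and other preventive). SAP 9.4.1 says drop-down and free-text names are all coded.
5. Add to SAP 6.3.1.3 a sensitivity analysis that repeats the main primary model without these subjects.
6. Leave the SAP 9.4.2 count and stratum 2 unchanged. Recoding after randomisation would create discrepancies with the RTSM strata and flag subjects as deviations who were eligible under the text in force.

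The cost is a few lost candidates if recruitment is still open, short wording changes, and one extra analysis. No new data are needed.

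Items 1 to 3 help only subjects not yet enrolled. Items 4 and 5 can be done whatever the state of recruitment, provided they are settled before the blind is broken.
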